11. STATISTICAL ANALYSIS

The baseline corrected AUC for carotenoids will be calculated by the trapezoidal approach, using the PK functions plug-in for Microsoft Excel. Negative values, if occurring, will be included as such.

Mean AUC between the test meals will be compared by a repeated measures ANOVA design (i.e. each subject will be compared against himself at 3 time points), followed by post-hoc test comparisons (Fisher protected LSD test) given a significant Fisher-F test. No log-transformation will be carried out, but AUC values will be baseline corrected. Thus, a model with the observed dependent factor baseline-corrected-AUC for each carotenoid (lycopene, beta-carotene) and the triglycerides will be run, with subject, randomization sequence, test meal as fixed factor and baseline carotenoid concentration as a covariate.

Normal distribution will be verified by Q-Q-plots and Kolmogorov-Smirnoff tests.

Non parametrical analysis (Friedman tests followed by individual t-tests) may be chosen in case data is not normally distributed, though based on earlier studies data normally follows normal distribution. Log-transformation will not be carried out.

P-values below 0.05 will be interpreted as statistically significant (2-tailed). Data analysis will be performed with SPSS 19.0 for Windows (SPSS Inc., Chicago IL).

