5.1 Outcome definition

Primary outcomes:

Beta-carotene and lycopene

Beta-carotene and lycopene will be measured in the plasma triacylglycerol rich lipoprotein (TRL) fraction in μM at baseline (0h) and 2h, 3h, 4h, 5h, 6h, 8h, 10h after test meal intake. Using non-compartmental analysis, repeated measures over time of carotenoids will be summarised as postprandial AUC (trapezoidal approach) using the PK functions plug-in for Microsoft Excel and will be validated in a statistical software such as R or SAS system. Of note, it is planned to baseline-subtract all further concentrations (hours 2-10), and to also subtract potentially occurring negative values from the AUC.

Baseline concentrations will be included as co-variates into the linear mixed model.

Secondary outcomes:

Triglycerides

Triglycerides will be measured in the plasma in mg/dL at baseline (0h) and 2h, 3h, 4h, 5h, 6h, 8h, 10h after test meal intake. Using non-compartmental analysis, repeated measures over time of triglycerides will be summarised as postprandial AUC (trapezoidal approach) using the PK functions plug-in for Microsoft Excel and will be validated in a statistical software such as R or SAS system.

Minor abundant carotenoids:

Isomers of beta-carotene and lycopene will be treated as the all-trans native form, i.e. all chromatographic peak area will be combined if isomers are identified in the plasma-TRL fraction.

If alpha-carotene or other carotenoids such as lutein and beta-cryptoxanthin can be measured (if chromatographic sensitivity is sufficient), AUC in the TRL fraction will also be determined, as described for beta-carotene and lycopene.

They will be accounted for in the analyses as secondary outcomes with similar analysis methodology

Total carotenoids will be produced by summing up all carotenoids measured and analysed as the primary endpoint

Carotenoids after colonic digestion:

Native carotenoids after colonic digestion, as well as excreted degradation products such as apo-carotenoids will be investigated, as far as the analytical capabilities allow. As no previous data exists in this respect, this part will be of highly explorative character.

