5.2 Analysis methods

The primary endpoint, AUC of either lycopene or beta carotene will be analysed using a linear mixed model using randomization sequence and treatment (test meal) as fixed terms and patient within sequence as a random term taking into account the cross-over design as described in chapter 5 of "Cross-Over Trials", Senn (2002). Baseline will be included as a co-variate.

Assumptions of normality and equality of variance will be verified by normality plots and boxplots, respectively. If data is non- normally distributed, log transformation will be attempted.

Non-parametrical analysis (Friedman tests followed by Wilcoxon- Mann- Whitney test) may be chosen in case data is not normally distributed, if log-transformation is not successful, though based on earlier studies data normally follows normal distribution.

The secondary endpoints - triglycerides, and if feasible additional carotenoids (see 5.1 above) will be analysed by the same methodology.

A linear mixed model will be first performed for each main outcome, with either baseline corrected AUC of lycopene or beta-carotene as the observed, dependent variable, and randomization sequence, test-meal as the independent variable (fixed factor) and patient within sequence as random factor. Pairwise comparisons of the intervention will be performed by means of Tukey's post-hoc test. Additionally, sensitivity analysis with the original outcomes (lycopene or beta-carotene) as dependent, randomization sequence, test meal and baseline concentration of the outcome as fixed factors and patient within sequence as random factor. 95% confidence intervals will be reported for the main outcomes.

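### Protocol 11 puts baseline carotenoid into the triglyceride model; the covariate should be the same visit's 0 h triglyceride, and the SAP should say so explicitly (minor)

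*Protocol*

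**What the plan says.** **Protocol 11.** The dependent variable is the "observed dependent factor baseline-corrected-AUC for each carotenoid (lycopene, beta-carotene) and the triglycerides will be run". The same sentence ends with "test meal as fixed factor and baseline carotenoid concentration as a covariate". No other covariate is given, and nothing separates the triglyceride model from the carotenoid models. The section also says "No log-transformation will be carried out, but AUC values will be baseline corrected", while its sentence on deriving the AUC speaks only of carotenoids: "The baseline corrected AUC for carotenoids will be calculated by the trapezoidal approach".

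**SAP 5.1.** For beta-carotene and lycopene, "it is planned to baseline-subtract all further concentrations (hours 2-10"), and baseline concentrations enter the mixed model as covariates. The triglyceride paragraph says "Triglycerides will be measured in the plasma in mg/dL at baseline (0h") and at the seven later times, and that "repeated measures over time of triglycerides will be summarised as postprandial AUC (trapezoidal approach"). It mentions neither subtraction nor a covariate.

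**SAP 5.2.** The first paragraph gives the primary model and lists baseline as a covariate. A later paragraph says that triglycerides are analysed in the same way. The last paragraph restates the main model with sequence, test meal and patient within sequence, but no baseline. It then adds a "sensitivity analysis with the original outcomes (lycopene or beta-carotene) as dependent", and only there is the covariate described as the baseline of the outcome itself.

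**Data.** Protocol Table II has triglycerides measured at 0 h and at the postprandial times of each clinical visit.

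**The concern.** A baseline covariate in this cross-over is useful because the subject term removes stable differences between men but not the variation in one man's fasting level from visit to visit. Only that visit's own triglyceride value measures this variation directly. A programmer who follows Protocol 11 to the letter would fit a carotenoid value instead. He would also have to choose which one, since two carotenoids are modelled and the sentence does not say.

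The SAP does not settle the matter in so many words. Analysts could defend a raw or a subtracted AUC, with the triglyceride baseline, a carotenoid baseline or none, and would get somewhat different estimates. At stake are precision and pre-specification for the three triglyceride contrasts in SAP 2.7. Protocol section 7 intends the triglyceride response to give insight into gastro-intestinal passage time and absorption.

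**Working it through.** **The plan's own figure.** The documents give no power or precision figure for triglycerides. The stated power is for the carotenoid AUC (SAP 2.6): difference 4%, SD of paired differences 4%, N = 24, two-sided level 0.05/6 = 0.0083. A noncentral t calculation with noncentrality (4/4)·√24 = 4.90 and N − 6 = 18 degrees of freedom gives 96.2%, against 96% stated. At N = 18 it gives 83.5%, against 83%. The figure reproduces, and this point does not depend on it.

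**Step 1: how the fasting value enters the AUC.** Sampling is at 0, 2, 3, 4, 5, 6, 8 and 10 h (SAP 2.9). The trapezoid weights are 1, 1.5, 1, 1, 1, 1.5, 2 and 1, which sum to 10 h. Let b be a man's visit-specific deviation in fasting triglyceride, β the share of it that persists through the day, and R the remaining within-man variation in AUC. Then

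- raw AUC = 10βb + R
- subtracted AUC = raw AUC − 10b = −10(1 − β)b + R.

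A raw AUC keeps too much of the fasting level and a subtracted AUC over-corrects, unless β = 1.

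**Step 2: with b as a covariate the two outcomes agree.** They differ by exactly 10b, so with b in the model the difference goes entirely into the slope for b. The meal contrasts are the same; a simulation of the design found differences below 1e-10. This holds on the untransformed scale only. It would fail under the log-transformation that the SAP allows as a fallback.

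**Step 3: size.** The inputs are assumptions, because the documents give none: SD(b) = 20-30 mg/dL, SD(R) = 150 mg/dL·h, β = 0.4-0.7. With 24 men each taking all three meals, SE = √(2/24) × within-man SD = 0.2887 × within-man SD.

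With the 0 h triglyceride covariate: 0.2887 × 150 = 43.3. A simulation of 4,000 trials gave 44.1; the small excess is the cost of estimating the slope.

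Without it, the within-man SD is √(150² + (10(1 − β)·SD(b))²) for the subtracted AUC and √(150² + (10β·SD(b))²) for the raw AUC:

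| SD(b) | β | Subtracted: SD, SE | Raw: SD, SE |
|---|---|---|---|
| 20 | 0.4 | 192.1, 55.5 | 170.0, 49.1 |
| 20 | 0.7 | 161.6, 46.6 | 205.2, 59.2 |
| 30 | 0.4 | 234.3, 67.6 | 192.1, 55.5 |
| 30 | 0.7 | 174.9, 50.5 | 258.1, 74.5 |

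Against 43.3, the subtracted AUC is 8% to 56% less precise (46.6/43.3 and 67.6/43.3) and the raw AUC 13% to 72% (49.1/43.3 and 74.5/43.3). Simulating the subtracted AUC with an unrelated carotenoid covariate gave 47.6 to 68.1 against 44.1, or 8% to 54%. At β = 1 the subtracted SD is 150 and nothing is lost. The raw AUC at SD(b) = 20 then has SD √(150² + 200²) = 250 and SE 72.2, which is 67% larger.

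**Step 4: a second set of assumptions.** Let s be the ratio of the within-man SD of the 0 h value to that of the 10 h mean, and ρ their within-man correlation. Relative to a raw AUC, the variance is 1 + s² − 2ρs after subtraction and 1 − ρ² with the covariate.

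| s | ρ | Subtracted | Covariate | SE ratio |
|---|---|---|---|---|
| 0.5 | 0.3 | 0.95 | 0.91 | 1.02 |
| 0.5 | 0.5 | 0.75 | 0.75 | 1.00 |
| 0.5 | 0.7 | 0.55 | 0.51 | 1.04 |
| 1.0 | 0.3 | 1.40 | 0.91 | 1.24 |
| 1.0 | 0.5 | 1.00 | 0.75 | 1.15 |
| 1.0 | 0.7 | 0.60 | 0.51 | 1.08 |

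Here subtraction alone costs 0% to 24% in SE. Adding an unrelated carotenoid covariate to the raw AUC gave simulated variances of 1.01 to 1.04 times those without it, so it brought no gain.

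**The case against.** A reader might infer that the triglyceride endpoint is nowhere adjusted for its own baseline. The documents do not support that. The Protocol 11 sentence that names the carotenoid covariate also makes the triglyceride outcome a baseline-corrected AUC, and subtracting the 0 h value is itself an adjustment.

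Nor does SAP 5.1 prescribe a raw triglyceride AUC; it is silent, and other text helps to fill the gap. SAP 2.3 introduces triglycerides as a further AUC and gives the plasma matrix as the difference, shortly after SAP 2.2 has set out subtraction and a baseline covariate. SAP 2.1 refers remaining procedures to the protocol. SAP 5.2 lists baseline without tying it to a carotenoid before applying the method to triglycerides, so the triglyceride baseline is the natural reading.

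All of that stands, and it narrows the point. It does not remove it. The covariate named in Protocol 11 is still the wrong analyte for this outcome. The SAP reaches the right one only by inference, and the last paragraph of 5.2 drops baseline from the main model.

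The size can also fairly be challenged. The upper end for the subtracted AUC comes from one corner of an assumed grid (SD 30, persistence 0.4), and the second set of assumptions gives a smaller loss. The simulations included a period effect that neither document's model contains. In the complete, balanced design meals are orthogonal to periods, so this hardly affects the comparison.

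**Conclusion.** The point holds as a minor one. Protocol 11 names a covariate that does not belong in the triglyceride model, and the SAP implies the right covariate without stating it or saying whether the triglyceride AUC is subtracted.

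The consequence is a possible loss of precision on a secondary endpoint for which no power is claimed. It should not be read as bias: meal order is randomised, the subject term removes stable differences between men, and an irrelevant covariate costs about one degree of freedom.

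Under the first set of assumptions the standard error is about 44 mg/dL·h with the triglyceride covariate, about 47-68 under Protocol 11 as written, and about 49-75 if a raw AUC were used without a triglyceride baseline. Under the second set the loss from subtraction alone is at most 24%, and at full persistence it is nil. The direction is well founded; the size is not known from the documents.

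**What to change.** - **Protocol 11:** replace the carotenoid covariate with the same visit's 0 h concentration of the outcome being analysed. For the triglyceride model this is 0 h plasma triglyceride, and no carotenoid value enters.
- **SAP 5.1:** state in the triglyceride paragraph that the outcome is the baseline-subtracted AUC from 0 to 10 h.
- **SAP 5.2:** state that the triglyceride model takes the 0 h plasma triglyceride of the same visit as a continuous covariate, and make the last paragraph's main model agree with the first paragraph on including baseline.

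The cost is a few sentences, with no new samples, visits or assays. On the untransformed scale the change also makes the choice between raw and subtracted AUC immaterial to the meal contrasts.

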12. VALORIZATION OF STUDY RESULTS

Benefits for the participant

1. Participants will be informed about their current health status as indicated by their blood biochemistry and anthropometric profile (please refer to Table II for the parameters analyzed in the enrolment phase).

2. All meals served in the trial will be free of charge.

3. Participants will receive for their participation in the study a total of 300€ and a total of 400€ as compensation if also stool samples will be collected. The value of compensation was based on similar previous trials such as the CNER evaluated BIOCAR study.

Benefits for the society in general

This nutritional postprandial study financed by the Luxembourgish FNR (*Fonds National de la Recherche*) is the extension of the work already carried out by our group within the BIOCAR study, studying the influence of divalent minerals on the bioavailability of carotenoids, which was the first nutritional postprandial study carried out in Luxembourg.

An additional asset of this study is the continued implication of the LIH's Clinical and Epidemiological Investigation Centre towards the conduction of further nutritional studies and will lay the foundation for future studies in this direction, which could move toward more long term dietary interventions, and perhaps including larger numbers of participants. Also, this would be the first nutritional study investigating the influence of proteins on the bioaccessibility and bioavailability of carotenoids.

A healthy diet should not only be of healthy composition, it is also important that potential health beneficial compounds are bioavailable, i.e. they should be absorbed to a sufficient extent from the diet to be used for specific functions by the human body. However, very little information is available on the bioavailability of carotenoids in the presence of proteins.

We are convinced that this study will allow us to obtain information about the absorption and bioavailability of carotenoids from a carotenoid-rich meal when consumed together with supplemented protein. The obtained information would be an important contribution for developing an improved healthy diet for the average consumer that would enhance carotenoid absorption and mitigate digestive losses as much as possible.

The influence of proteins on carotenoids during digestion, uptake, and absorption has never been systematically studied. However, in sight of the situation that only few food items contain both proteins and carotenoids, it would be interesting to see if carotenoid absorption can be increased when combining fruits/vegetables with protein rich meals. This would surely constitute a question of interest for many consumers, notably vegetarians/vegans, but also for subjects not consuming many animal-based foods (rich in vitamin A), who rely on vitamin A intake by carotenoid consumption, such as in many developing countries.

13. RISKS AND POSSIBLE INCONVENIENTS OF THE STUDY

Risk for subjects:

The risks associated with this study protocol in the population described above are minimal. No invasive procedures will be used in this study apart from peripheral blood drawings. There are minor risks associated with venipuncture such as mild discomfort, fainting or bruising. Less commonly, a small clot, swelling of the vein, infection, or bleeding may occur at the site of puncture. All venipuncture procedures and blood samplings will be performed by a trained nurse from the CIEC.

Participants will be asked in advance for any kind of food allergies or intolerances (e.g. gluten or milk) that are not compatible with the test meals and midday and evening snacks, given throughout the days of the trial. Any participant

showing new medical problems that are not easily explained (e.g. colds) or that requires the use of medication (e.g. antibiotics) will be withdrawn from the study.

Indeed, allergies against various proteins, including those that can be selected, have been reported. For soy protein isolate, two proteins β -conglycinin and glycinin have been suggested to be the major fractions containing allergens [32, 33], affecting approximately 0.4% of children, making soy allergy about half as common as peanut allergy [34]. The latter allergy is caused by eleven allergenic proteins [35] and Ara H2 protein is the most potent allergen [36]. However, in refined peanut oil, this protein is not expected to be present [37]. For whey protein isolate, α -lactalbumin and β -lactoglobulin have been stated as the main allergens, affecting up to 1–3% of adults and 3–8% of infants [38] [39]. When α S1-casein seems to be a major allergen of sodium caseinate according to IgE and T cell recognition data [40], and affecting about 5-6% of young children [41], α 2 chain has been reported as a main allergen of gelatin bovine, and affecting 3% of children with a history of beef meat allergy [42]. We will carefully question the participants regarding any allergies that they may have encountered and exclude any subject with a history of allergic reactions toward peanut, soy, or milk protein.

Carotenoids in amounts similar as consumed in our study are consumed within daily diets and have been served, also within fruits and vegetables in previously in other human studies (Unlu et al. 2005; Bohn et al. 2011, Borel et al, 2017) with no observed adverse effects.

Drop-outs and power calculation:

Participants are free to withdraw from the study at any moment if they desire to do so. However, we will try our best in terms of follow-up to keep subjects in the study. However, should several subjects opt to leave the study, we would still, even with only ca. 12-15 subjects, reach sufficient statistical strength, i.e. power, to see a reasonable difference in absorption, if it exists.

Power calculation:

For example, a cross-over trial with four subjects in each of six sequences will have 95% power to detect a difference of 20% (e.g. fractional absorption 20 vs. 24%) at the 5% level (two-sided) if the SD of paired differences within subjects is 20%. A design with four subjects per sequence makes ample allowance for possible drop-outs and also for adjusting the type I error rate for individual contrasts to allow for multiplicity (<http://www.quantitativeskills.com/sisa/calculations/samsize.htm>). As each subject will act as his/her own control, this could be seen as a realistic estimate.

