9. PARTICIPANTS

Number of Participants

Twenty four male individuals from or living in the region of Luxembourg will be recruited for this study. The number of participants is based on a randomized block design, constituting of 6 blocks of 4 subjects, each will be served different sequences of test meals (A, B, C/A, C, B/B, C, A/B, A, C/C, A, B/C, B, A) in order to cancel out any potential effect of sequence of meals (See scheme of test meal sequences in Figure 2).

Our aim would thus be to recruit 24 subjects, and try our best in terms of follow-up and interaction to keep them in the study. However, should several subjects opt to leave the study, we would still, even with only ca. 15 subjects, reach

sufficient statistical strength to see small differences in absorption in this cross-over study. For example, a difference in fractional absorption between 10% and 8% could be resolved already in a pairwise design with a SD of absorption difference of ca. 2.5% for an alpha of 0.05 and a power of 80% (<http://biomath.info/power/prt.htm>). As each subject will act as his/her own control, this could be seen as a realistic estimate. The reason for recruiting male subjects only is that carotenoid plasma concentrations are likely influenced by the monthly cycle of women [29], and we preferred not to undergo any risk in this regard – this position was also accepted by the FNR (Grant CAROPROT, C16/BM/11320230).

Inclusion criteria

- healthy and free living;
- men;
- age between 20 and 50 years old;
- Body-Mass-Index (BMI) <30 kg/m²
- non-smokers (abstinent for more than 2 years);

Exclusion criteria:

- suffering from any metabolic disease that may cause digestive disturbances (such as Crohn's disease or colitis);
- malabsorption disorders;
- BMI over 30 kg/m²;
- hyperlipidaemia (triglycerides and total cholesterol over 200 mg/dl)
- any individuals following a special diet that is not compatible with wash-out periods or test meals (vegetarian, gluten-free or diabetic);
- regular consumption of more than 5 portions (80-100 g) of fruits and vegetables per day;
- being on medical treatment or consuming any medication for chronic conditions or recent illness (e.g. antibiotics);
- consuming regularly dietary supplements;
- abnormally high or low values of plasma circulating carotenoids;
- tobacco smoking;
- frequent alcohol consumption (over 2 glasses per day);
- food allergies or intolerances that are not compatible with test meals (e.g. gluten or milk intolerance);

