2.6 Sample Size

It is assumed that two different outcomes will be tested as dependent variables and all pairwise comparisons will be performed. First lycopene and then beta-carotene will be tested. This will lead to three statistical tests per carotenoid readout: with the original alpha risk of 0.05 the corrected alpha risk would then be $0.05/6=0.083$ i.e. 0.83%. The Bonferroni adjustment will be used to keep the family-wise error at the specified error level and thus with the total number of pairwise comparisons equal to 6 each pairwise test is at the two-sided 0.83% significance level.

Area under the time – carotenoid concentration is assumed as main outcome for the sample size calculation.

When there are 2 outcomes (lycopene and beta-carotene), 3 treatments and a sample size of 4 in each of the 6 sequences, a 6x3 Williams Crossover inequality test of paired differences will have 96% power to detect a minimum difference of 4% of the area under time curve (AUC) (difference between 20% and 24% of AUC) or greater, assuming that the standard deviation of the paired differences is 4% at the 0.83% significance level. This leads to a total sample size of N=24 participants.

In case of one drop-out per sequence (n=3 per sequence), the power will reduce to 83%, which will still provide sufficient statistical strength. Sample size calculation was performed in nQuery 8 (version 8.3.1.0).

[figure not shown]

Figure 3 Power (%) vs. Sample Size per Sequence; minimum difference = 4%, SD = 4%, significance level = 0.8%

Figure 4 Power (%) vs. Minimum Expected Difference; n per sequence = 4, $SD = 4\%$, significance level = 0.8%

[figure not shown]

Figure 5 Power (%) vs. Standard deviation; $n=4$ per sequence, mean difference = 4%, significance level = 0.8%

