3.1 P- values and multiplicity adjustment

As two statistical tests will be performed per main outcome (beta-carotene and lycopene), the total number of comparisons will be 6 (3 x 2) and therefore multiplicity correction will be applied. A Bonferroni corrected p-value will be used at that level: $\frac{\alpha}{2} = \frac{0.05}{2} = 0.025$. For the three post-hoc tests within each outcome (test meals vs. control), Tukey's post hoc test will be applied.

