4.3 Withdrawal/ follow-up

Participants are free to withdraw from the study at any moment if they desire to do so. However, we will try our best in terms of follow-up to keep subjects in the study. Any participant showing new medical problems that are not easily explained (e.g. colds) or that requires the use of medication (e.g. antibiotics) will be withdrawn from the study.

Subjects that have at least completed 2 clinical days will be kept for statistical analysis, and given that subjects agree to keeping their data. Otherwise, the cases will be removed from analysis.

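### Protocol 13 states 95% power where its inputs give about 99.7%, and its 12-15 subject drop-out assurance holds at an unadjusted 5% level but not, at the 12-subject end, at the SAP's 0.83%

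*Protocol*

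**What the plan says.** Protocol section 13 (power calculation) takes the full design, 24 men spread evenly over the sequences, and claims that it "will have 95% power to detect a difference of 20% (e.g. fractional absorption 20 vs. 24%) at the 5% level (two-sided"), given an SD of paired differences of 20%. Just before this, on drop-outs, it says that the trial would, "even with only ca. 12-15 subjects, reach sufficient statistical strength, i.e. power, to see a reasonable difference in absorption". It attaches no effect size, SD, level or power target to that range.

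Protocol section 9 makes a similar statement for about 15 subjects and does give its inputs: absorption of 10% against 8%, "with a SD of absorption difference of ca. 2.5% for an alpha of 0.05 and a power of 80" percent.

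Protocol section 11 tests at two-sided 0.05, with meal comparisons "followed by post-hoc test comparisons (Fisher protected LSD test) given a significant Fisher-F test". There is no per-contrast adjustment beyond the F test.

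SAP 2.6 plans on a difference of 4% (20% against 24%), "assuming that the standard deviation of the paired differences is 4% at the 0.83% significance level", and states 96% power with 24 subjects. On losses it says: "In case of one drop-out per sequence (n=3 per sequence), the power will reduce to 83" percent. It gives nothing below 18 subjects.

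SAP 3.1 sets 0.025 per carotenoid ("A Bonferroni corrected p-value will be used at that level") and applies Tukey's test to the three meal comparisons. SAP 5.2 fits a linear mixed model.

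**The concern.** Two things look wrong.

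First, the Protocol and the SAP use the same number of subjects and the same ratio of difference to SD (20/20 and 4/4, both 1.0). The Protocol reports 95% at 5%; the SAP reports 96% at 0.83%. Power cannot be lower at the looser level, so one figure must be wrong before any modelling choice is made.

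Second, the Protocol's tolerance for drop-out reaches down to 12 subjects, while the SAP's stops at 18. The SAP's level is about one sixth of the Protocol's, and its text does not withdraw the Protocol's statement. If losses were heavy, someone relying on Protocol 13 could treat a trial with about 12 completers as adequately powered and read a non-significant contrast as absence of effect.

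**Working it through.** **Inputs.** n = 24, ratio 1.0, two-sided 0.05 (Protocol 13). Ratio 2/2.5 = 0.8, n = 15, alpha 0.05, power 80% (Protocol 9). Ratio 4/4 = 1.0, alpha 0.05/6 = 0.0083, n = 24 and 18 (SAP 2.6). Family-wise 0.025 with Tukey over three means (SAP 3.1).

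**Method.** Two-sided noncentral t: noncentrality = ratio × √n, and power = P(|T| > t(1 − alpha/2, df)). The documents do not state the degrees of freedom, so three choices are shown: n−6 (subjects minus sequences), n−1 (plain paired test) and 2n−4 (closest to the SAP 5.2 mixed model).

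**Step 1: reproduce the SAP's figures.** At 0.83%, ratio 1.0 and df n−6:
- n = 24: noncentrality √24 = 4.90, df 18, critical t 2.96, power 96.2% (SAP: 96%).
- n = 18: noncentrality √18 = 4.24, df 12, critical t 3.15, power 83.5% (SAP: 83%).

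So df n−6 matches SAP 2.6.

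**Step 2: try to reproduce the Protocol's 95%.** At 5%, ratio 1.0 and n = 24, power is 99.61% (df 18), 99.68% (df 23) or 99.77% (df 44). None is near 95%. About 95% is what 16 subjects (94.9%, df n−6), 15 subjects (94.9%, df n−1) or 14 subjects (94.8%, df 2n−4) would give.

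**Step 3: power with fewer subjects.** Order of entries: df n−6 / n−1 / 2n−4.

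| Completers | 5%, ratio 1.0 | 5%, ratio 0.8 | 0.83%, ratio 1.0 |
|---|---|---|---|
| 24 | 99.6 / 99.7 / 99.8% | 96 / 96 / 97% | 96 / 97 / 98% |
| 18 | 97 / 98 / 98% | 88 / 89 / 91% | 84 / 88 / 91% |
| 15 | 93 / 95 / 96% | 79 / 82 / 85% | 68 / 77 / 83% |
| 12 | 82 / 88 / 91% | 64 / 71 / 75% | 44 / 61 / 70% |

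At 5%, the 12-15 statement holds at ratio 1.0 (82-96%), and Protocol 9's 15-subject example is about right (79-85%). At ratio 0.8 the 12-subject end would fall short even at 5%, but Protocol 13 does not tie its range to that ratio.

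**Step 4: the SAP 3.1 rule.** The critical value is q/√2, where q is the studentized range quantile for three means; df 2n−4, ratio 1.0.
- Tukey at family-wise 0.025: n = 12, critical value 2.86, power 72%; n = 15, critical value 2.80, power 85%.
- Tukey at family-wise 0.05: n = 12, critical value 2.53, power 81.5%; n = 15, critical value 2.48, power 91%.

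**Step 5: size of the gap at 12.** At 0.83%, 80% power with 12 completers needs a ratio of 1.10 on df 2n−4, or 1.43 on df n−6, against the planned 1.0. With an SD of 20%, that is a difference of about 22% (1.10 × 20) or 29% (1.43 × 20) instead of 20%.

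**The case against.** The strongest reply is that Protocol 13 is right on its own terms. It promises power for a reasonable difference, names no threshold, and belongs to a plan that tests at 5%. The shortfall appears only when Protocol 9's 80%, the SAP's level and a ratio of 1.0 are put together, and no document makes that combined promise. This stands. It limits the point to one of carry-over: the assurance does not transfer to the SAP's level.

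Second, the lowest figures (44% and 68%) rest on df n−6, which matches the SAP's planning but not its mixed model. On mixed-model df the figures are 70% and 83%, so 15 subjects pass. This also stands.

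Third, SAP 3.1 does not say at which family-wise level Tukey is run. A reader might infer that 12 subjects fall short under every possible rule. The documents do not support that: with Tukey at 0.05 within each carotenoid, 12 subjects reach about 82%, although that reading sets aside the 0.025 correction in SAP 3.1.

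Fourth, "Subjects that have at least completed 2 clinical days will be kept for statistical analysis". A two-visit subject is worth about half a completer, assuming the last visit is the one missed and losses are even over sequences. Twelve completers plus six such subjects then have the power of 15 (83-85% on mixed-model df).

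A reader might also infer that the trial is too small, or that Protocol 13 contradicts itself by claiming room for both drop-outs and multiplicity adjustment. Neither follows. The 95% is understated, and the multiplicity remark concerns four subjects per sequence, where power at 0.83% is 96-98%.

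**Conclusion.** The 95% in Protocol 13 is wrong as written: its inputs give about 99.7%, and it conflicts with the SAP's 96% at a stricter level. The error is conservative and N = 24 stands.

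The assurances for 12-15 and about 15 subjects are broadly right only at the unadjusted 5% level. Against Protocol 9's 80%, 12 completers are not supported at the SAP's 0.83% (44-70%) or with Tukey at 0.025 (72%). Fifteen are adequate on the planned mixed model (83-85%) but not on the df behind SAP 2.6 (68%).

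This assumes that the Protocol's 20% SD is on the same relative scale as its 20% difference, as SAP 2.6's 4% and 4% suggest; equal variance for the three pairwise differences; and 80% as the benchmark, since Protocol 13 gives none. The point is minor: it concerns stated power and drop-out tolerance, not the design.

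**What to change.** In Protocol 13, replace 95% with about 99.7% at the 5% level, or cite the SAP's 96% at 0.83%.

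In Protocol 13 (12-15 subjects) and Protocol 9 (about 15), either label the statements as unadjusted 5% figures, or replace them with power at the SAP's level for 18, 15 and 12 completers, naming the df used. If the 12-15 range is kept, give the difference, SD and level it rests on.

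These are wording changes. Sample size, visits and assays are unaffected; the only cost is a less favourable stated tolerance to drop-out.
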